1. FMT procedure-related adverse events from colonoscopy/sigmoidoscopy or enema (e.g. perforation, sedation related)

2. FMT material-related adverse events (e.g. transmissible infection, allergic reaction) 3. Short-term safety: Both solicited and unsolicited adverse events will be recorded by, telephone follow-up at Day 3 (+/- 2 days) and clinical assessment at Week 6 (+/- 2 weeks).

4. Long-term safety evaluations will focus on any new medical conditions/medications, which may be related or unrelated to FMT. This information will be elicited at the 6 month and 12 month follow-up telephone call and documented.

VI-A. Adverse Events Reporting

A. Definitions

1. Adverse Event (AE)

An AE is any untoward medical occurrence in a patient or study subject administered FMT that does not necessarily have a causal relationship with this treatment. An AE can therefore be any unfavorable and unintended sign (including an abnormal laboratory finding), symptom, or disease temporally associated with the use of a FMT, whether or not related to the FMT.

• AEs may be new events or may be pre-existing conditions that have become aggravated or have worsened in severity or frequency.

• AEs may be clinically significant changes from baseline in physical examination, laboratory tests, or other diagnostic investigation (e.g. laboratory results, radiographic findings).

Pregnancy is not an AE; however, if a female subject becomes pregnant during the conduct of the study, the Investigator will notify Sponsor who is responsible for notifying the FDA.

2. Serious Adverse Event (SAE)

A serious adverse event is any adverse experience occurring during or after FMT that results in any of the following outcomes:

• Death

• Life-threatening experience

Note: An adverse event or suspected adverse reaction is considered "life-threatening" if, in the view of either the Investigator or Sponsor, its occurrence places the patient or subject at immediate risk of death. It does not include an adverse event or suspected adverse reaction that, had it occurred in a more severe form, might have caused death.

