• Requires inpatient hospitalization or prolongation of existing hospitalization Note: Adverse events requiring hospital admissions that are less than 24 hours in duration do not meet this criterion. A scheduled hospitalization for a pre-existing condition that has not worsened during participation in the study does not meet this criterion. Pre-planned hospitalizations for an elective medical/surgical procedure or routine check-ups do not meet this criterion. Admission for CDI relapse will not be included in this definition.

- Results in persistent or significant disability or incapacity
- Results in a congenital anomaly or birth defect

• Results in an important medical event

Note: Important medical events are those that may not be immediately life threatening or result in death or hospitalization but may jeopardize the patient or may require intervention to prevent one of the outcomes listed in the definition above.

3. Planned Hospitalization

A hospitalization planned prior to FMT is to be considered a therapeutic intervention and not the result of a new SAE. If the hospitalization or procedure is executed as planned, it will be recorded in the subject's medical history or procedures. However, if the event/condition worsens during the study, it must be reported as an AE.

4. Adverse reaction

An adverse reaction means any adverse event caused by FMT. Adverse reactions are a subset of all suspected adverse events for which there is reason to conclude that FMT caused the event.

5. Suspected Adverse Reaction

Suspected adverse reaction means any adverse event for which there is a reasonable possibility that FMT caused the adverse event. For the purposes of IND safety reporting, 'reasonable possibility' means there is evidence to suggest a causal relationship between FMT and the adverse event. A suspected adverse reaction implies a lesser degree of certainty about causality than adverse reaction, which means any adverse event caused by a therapy.

6. Unexpected

An adverse event or suspected adverse reaction is considered "unexpected" if it is not listed in the Investigator brochure or is not listed at the specificity or severity that has been observed; or is not consistent with the risk information described in the general investigational plan or elsewhere in the current application.

VI-B. Solicited Adverse Events

Short-term

The following short-term AEs and their associated intensities will be solicited:

- Fever
 - Mild 37.7-38.6°C

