• The AE is more likely explained by FMT than by another cause

VI-E. Reporting Safety Observations by the Investigator to the Sponsor

1. Reporting of Non-serious AEs

All AEs, regardless of seriousness, severity, or causal relationship to FMT, will be recorded in the AE section of the subject case report form.

2. Reporting of FMT Exposure during Pregnancy

If a female subject or the female partner of a male subject becomes pregnant during the course of study, the Investigator must report this occurrence to the Sponsor within **72 hours** of becoming aware of the pregnancy. The Investigator is required to follow up on the pregnancy until it has completed. The outcome of the pregnancy and the status of the newborn (if applicable) will be reported within 24 hours of becoming aware. If the female partner of a male subject becomes pregnant, the Investigator must obtain consent to collect pregnancy information (including the status of the newborn, if applicable).

3. Reporting of Safety Observations by the Investigator

Any occurrence of the following events or outcomes must be reported expeditiously by the Investigator or qualified designee to the local IRB and to the Sponsor, who will be responsible for reporting the event to the FDA:

- 1. SAE related to FMT material
- 2. Death of a subject related to FMT material

The site Investigator is to report any safety observations from the list above to the Sponsor within **72 hours** of becoming aware of the event, who in turn, will notify the FDA. Any observation that is also an AE will be recorded on the subjects case report form along with any actions taken. If not all information is available at the time of initial report, follow up SAE reports will be completed and submitted.

Any occurrence of the following events or outcomes must be reported by the Investigator or qualified designee to the local IRB and to the Sponsor, who will be responsible for reporting the event to the FDA:

- 1. SAE unrelated to FMT material
- 2. Death of subject unrelated to FMT material
- 3. Hospitalization related to CDI
- 4. New or worsening medical condition, or new medications

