A serious and unexpected adverse reaction is a SAE as determined by the Investigator or Sponsor, as defined previously, in combination with unexpected, defined as not being listed in the Investigator Brochure. At the request of the FDA, it will also include any documented infectious disease, defined as a new onset infection in the recipient after FMT and the infection present in the safety aliquot, which is a sample of the exact specimen that was transferred to the patient.

B. Findings from other sources

The Sponsor will also expeditiously report any findings from clinical, epidemiological, or pooled analysis of multiple studies or any findings that

suggest a significant risk in humans exposed to FMT and thought related to the material.

C. Increased occurrence of serious suspected adverse reactions related to FMT material

The Sponsor will report any clinically important increase in the rate of a serious suspected adverse reaction over that listed in the protocol.

VI-G. Halting Rules

Specific safety findings will result in temporarily suspending enrollment until a safety review is convened, the objective of which is to determine whether the study should continue per protocol, proceed with caution, be further investigated, be discontinued, or be modified and then proceed. Suspension of enrollment, for a particular group, such as colonoscopy group, or for the entire study, is another potential outcome of a safety review.

Subsequent review of serious, unexpected, and related AEs by the Data and Safety Monitoring Board (DSMB), IRB, the Sponsor, or the FDA or relevant local regulatory authorities may also result in suspension of further trial interventions/administration of FMT at a site. The FDA and study Sponsor(s) retain the authority to suspend additional enrollment and study interventions/administration of FMT for the entire study, as applicable.

Findings that will trigger a safety review are

- Death related to FMT material
- Confirmed transmission of a clinically concerning infection from donor to subject via FMT
- If one or more subjects experiences a serious, unexpected adverse event related to FMT material
- Significant increase in frequency of events theoretically related to FMT material (specifically, new diagnoses of inflammatory bowel disease). Discussion on threshold will be discussed with DSMB and will be on a disease specific basis.

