For individual subjects enrolled in the study: any subject who has an SAE related to FMT will be ineligible for a second FMT during the course of the study.

FDA/CBER will be notified by phone or fax within 48 hours if the study is halted for review.

VII. Minimizing Risks to Human Subjects

VII-A. Human Subjects Involvement, Characteristics and Design

1. IRB approval for stool donor program has been obtained; Local site IRB approval from *each* study center will be obtained subsequent to required FDA approval of IND.

2. Subjects will be given informed consent using the standard consent process for colonoscopy/enema. Additional theoretical risk for transmission of infectious agents, and other diseases and conditions will also be discussed.

3. Donors will be given informed consent and will tested for most common infectious agents. Individuals with communicable disorders or a history of high-risk behaviors will not be permitted to donate.

4. Protections against risk are provided in detail below.

A sample size of 150 patients will be recruited. These patients will have been treated at or referred to one of the study centers for management of recurrent CDI.

Additional sites may be asked to join this study as needed to expeditiously achieve the targeted enrollment. The initial study sites will include:

1. Brown University and Women's Medicine Collaborative Providence, Rhode Island

2. Indiana University Health University Hospital Indianapolis, Indiana

3. University of Virginia Health Systems Charlottesville, Virginia

4. Edward Hospital Naperville, Illinois

This will be an open-label, longitudinal cohort study with follow-up at Day 3, Week 6, Month 6 and Month 12. The estimated duration of this study is 24 months. No patient will be excluded from recruitment on the basis of ethnicity, race, or disability. Subjects are expected to range in age from 18-75. Subjects will all be outpatients and will likely have comorbidities. All subjects will be fully informed about the purposes of the study, and risks and benefits of the study, and informed consent for all phases of the study will be obtained. Patients who agree to participate will be free to withdraw from the project at any time.

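### No VI-G halting trigger covers a death caused purely by the delivery procedure, so such a death would not automatically suspend enrollment

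*Combined protocol and SAP*

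**What the plan says.** Protocol Section VI-G makes the pause automatic for listed findings: "Specific safety findings will result in temporarily suspending enrollment until a safety review is convened". The list has four items:

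1. "Death related to FMT material".
2. Confirmed donor-to-subject transmission of a clinically concerning infection.
3. "If one or more subjects experiences a serious, unexpected adverse event related to FMT material".
4. A significant increase in events theoretically related to the material, with new inflammatory bowel disease as the named case. The threshold is left for discussion with the DSMB.

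Section VI (Adverse Event Monitoring) separates two classes of event. Its first item is "FMT procedure-related adverse events from colonoscopy/sigmoidoscopy or enema (e.g. perforation, sedation related"; its second is events related to the material, such as a transmitted infection or an allergic reaction.

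Section VI-E sets two reporting tracks. Material-related SAEs and deaths go to the local IRB and to the sponsor, with 72 hours allowed for the sponsor. The slower track includes "Death of subject unrelated to FMT material". That also goes to the local IRB and the sponsor, but the sponsor deadline is 7 days and the sponsor informs FDA in the Annual Report.

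VI-G adds discretionary powers. Review of serious, unexpected and related events by the DSMB, IRB, sponsor or regulators may suspend FMT at a site, and FDA and the sponsor "retain the authority to suspend additional enrollment". Finally, "FDA/CBER will be notified by phone or fax within 48 hours if the study is halted for review".

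**The concern.** The procedure is how the study treatment is given, and the protocol recognizes its hazards. The hypothesis under Specific Aim 1 mentions procedure-related complications, and Section VII-B puts the physical risks of colonoscopy/sigmoidoscopy first among three areas of risk to subjects. VI-G even names suspension of the colonoscopy group as a possible outcome of a safety review. Yet no item on the trigger list names a procedural event, so nothing on that list would bring about such a review.

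What is at stake is prompt protection of the next subjects. A death from perforation, sedation or aspiration can point to a correctable problem with a site, an operator or a sedation practice. Under the current text, whether enrollment pauses while that is examined is left to judgment.

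**Working it through.** **Step 1. Check a purely procedural death against each VI-G trigger.** Take a death from perforation, sedation, bowel preparation or enema, with no contribution from the donor material.

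- Trigger 1 (death): limited to the material. Not met.
- Trigger 2 (transmitted infection): not met.
- Trigger 3 (serious, unexpected event): limited to the material. Not met.
- Trigger 4 (increased frequency): limited to events theoretically related to the material. Not met.

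Result: 0 of 4 triggers met.

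**Step 2. Ask whether the term for the material could be read to include the procedure.** Section VI lists the two classes separately, with different examples. The VI-G rule barring a subject from a second FMT refers to an SAE related to FMT, without the word material, so the protocol uses both a broader and a narrower term, and the triggers use the narrower one. One sentence in Section VII-A sets the endoscope beside donor stool when describing the material, but it is garbled, concerns dosing, and does not override the split in Section VI.

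**Step 3. Look for a mandatory pause elsewhere.** None was found in VI-E, VI-F or VII-E. The 7-day FDA report of unexpected fatal or life-threatening reactions in VI-F is limited to the material, and VII-E repeats that limit.

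**Step 4. Compare the reporting deadlines in VI-E.** A material-related death is due to the sponsor within 72 hours (3 days); a purely procedural death is due within 7 days. The difference is 7 − 3 = 4 days. It is a difference between maximum deadlines, not an expected delay.

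**Step 5. List the routes that remain.**

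- The local IRB receives the report under VI-E.
- VI-G review of serious, unexpected and related events is not confined to the material. It could reach a procedural death, since an event counts as unexpected if it "is not listed at the specificity or severity that has been observed" (VI-A, item 6).
- The sponsor and FDA may suspend the whole study (VI-G).
- The DSMB can meet off schedule, and reports of its quarterly meetings go to the IRBs and FDA (VII-E).

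All of these allow a pause; none requires one.

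**Step 6. Size.** The plan gives no figure to reproduce. From the plan: 150 subjects, with route at the physician's discretion. Assumed, because the documents give neither: a procedural death rate r of 0.01% to 0.1% per endoscopy, and n = 75 or 150 first endoscopies (half or all of the cohort).

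P(at least one death) = 1 − (1 − r)^n

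- n = 75: 1 − 0.9999^75 = 0.0075; 1 − 0.999^75 = 0.0723.
- n = 150: 1 − 0.9999^150 = 0.0149; 1 − 0.999^150 = 0.1394.

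The one related observation in the protocol (Section 9, III-A) is a death from aspiration at colonoscopy for FMT among 80 immunocompromised patients: 1/80 = 1.25%, exact 95% CI 0.03% to 6.8%. This trial excludes severely immunocompromised patients, so that rate is probably too high here and is not used above.

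**The case against.** The best defense is that the limit is deliberate. It recurs across VI-E, VI-F, VI-G and VII-E. The material comes from a stool bank with universal donors, so a hazard in the material could reach several sites, whereas a perforation or sedation death is more plausibly specific to a site or operator. Site-level suspension suits that case, and several bodies can order it. The protocol also treats endoscopic risk as standard, with the usual procedural consent. Much of this stands: the limit looks like a design choice, and a procedural death would not be ignored. It does not remove the gap, because a known risk can still signal something correctable and every remaining route is optional.

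Three stronger readings are tempting, and the documents do not support them.

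- A reader might infer that a material-related death stops treatment while a procedural one does not. A trigger suspends enrollment only, and only until a review is convened. Suspending FMT in subjects already enrolled is discretionary after any death, including a material-related one.
- A reader might infer that FDA would necessarily learn of a procedural death only from the Annual Report, or could never receive the 48-hour notice. DSMB reports go to FDA after each quarterly meeting, and the 48-hour notice also follows a discretionary halt.
- A reader might add repeat colonoscopies to the risk by taking 10% to 20% of subjects as non-responders. The 80-90% cure rate in Specific Aim 3 is a 12-month prediction that excludes patients needing further antibiotics. Repeat FMT is optional and follows non-response within 6 weeks, so that rate does not give the number of repeats.

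**Conclusion.** The point holds for deaths caused purely by the procedure. Such a death meets none of the four triggers, does not suspend enrollment by rule, and has a sponsor reporting limit 4 days longer than a material-related death. A death judged related to the material, including one of mixed cause, would still trigger the pause.

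The chance that the missing trigger would matter is about 0.7% to 7% with 75 first endoscopies and 1.5% to 14% with 150. Both the death rate and the route split behind these ranges are assumptions. Deaths after enema delivery or repeat colonoscopy are not counted. No endpoint or estimate is affected. This is a low-priority safety improvement.

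**What to change.** Add one item to the VI-G trigger list: *Death related to the FMT delivery procedure (endoscopy, sedation, bowel preparation or enema)*. List the same event among the 72-hour reports in VI-E. Review can use the existing DSMB and the group-specific or whole-study suspension outcomes already named in VI-G.

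The change takes one line in each section and needs no new committee. Its downside is a rare, short enrollment pause for a complication that ordinary endoscopy also carries. The pause is required only until the review is convened, and continuing unchanged is one of the outcomes VI-G allows. The added line would not itself stop FMT in subjects already enrolled.

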There have been no confirmed infectious complications directly attributable to FMT reported in the literature to date aside from a speculation about a norovirus case although the donor was untested for this.²⁹ There have been two FMT cases of bacteremia, although the strength of the association is unclear, and both patients did well on antibiotic therapy. However, since the process involves infusion of one person's "body fluids" into another person, transmission of an infectious agent or other disease or condition remains a theoretical possibility. From infusion of donor microbiome, the patient/subject could potentially acquire risk factors for chronic diseases such as diabetes or inflammatory bowel disease. Risks will be minimized by a rigorous donor selection process and evaluative studies on stool and blood of the donor to exclude transmission of infectious agents prior to FMT. Subjects will be informed that the treatment or procedure may involve these theoretical risks and additional risks that are currently unforeseeable. There have been reported cases of inflammatory bowel disease flares post-FMT, but it is unclear if this was attributable, and these patients have been excluded from this study. Infusion of fecal material containing a potential agent to which the subject is allergic is also a concern and so patients with a history of severe (anaphylactic) food allergy will be excluded from this study.

VII-C. Potential Risks to Donors

This study also involves individuals (donors) recruited to donate stool for FMT. There are 3 areas of risk to the potential stool donor.

These include:

 Physical risks related to laboratory testing and the stool collection protocol
 Psychological risks related to both revealing and potentially learning sensitive information during donor screening process

3) Risks related to confidentiality and loss of privacy.

OpenBiome volunteer donors will be utilized. In order to exclude donors at high risk of passing infection, a Donor Risk Factor Questionnaire (*Appendix* 2) will be administered. This questionnaire contains sensitive and potentially embarrassing questions

Additionally, prospective donors will be asked questions about their baseline health status and co-morbidities. Laboratory tests drawn as part of the screening process will include testing for HIV, viral hepatitis, and syphilis. These serologic results, if found to be abnormal, could cause psychological distress to the donor. However, the benefit of being made aware of a previously undiagnosed infectious condition outweighs this risk. Potential donors may experience psychological distress if they are excluded from donating stool based on these screenings.

Physical Risks to Donor:

Very Likely

• Blood drawing: pain, bruising, feeling faint, slight risk of infection

Nonphysical Risks to Donor:

Less Likely

• Embarrassment or psychological distress from answering questions

asked during the donor screening process.

• Psychological distress (guilt and embarrassment) if screening questionnaire or laboratory test results exclude the person from donation.

Unlikely

• There is also risk of compromising donor privacy through breach of data confidentiality of sensitive protected health information such as results of HIV or viral hepatitis testing.

VII-D. Protection against Risks to Subjects and Donors

Recruitment and informed consent

Participants will be recruited from study sites previously outlined. After a patient has been referred for recurrent CDI and determined to meet inclusion criteria, the clinician will introduce him/her to the research assistant, if applicable. The research staff or clinician will carefully explain all aspects of the study to a potential recruit, including the risks and benefits, and obtain participant's written informed consent.

- The research assistant or clinician will orally describe the material written in the informed consent document and answer any questions the participant may have.
- Participants will be reminded that they are not required to participate in the study and that they will receive the standard care provided by their physician

regardless of whether or not they choose to participate. Participants who give their consent will sign a copy of the document and will be given a signed copy of the informed consent document.

Recruits will be informed of the treatment commitment, amount and general types of assessments, the follow-up telephone interview procedures, and clinic visits. They will be given detailed descriptions of the colonoscopy or enema with FMT procedure. They will be informed of the requirements to submit stool specimens up to 3 days before, as well as 6 weeks, 6 months, and 12 months after the FMT procedure.

Potential donors who are healthy will be recruited to serve in a pool through an IRBapproved process. Each potential donor will then be contacted by the research staff and asked to participate in the donor consent process. Research staff will carefully explain all aspects of the study to a potential donor, including the risks and benefits, and obtain participants' written informed consent. Recruits will be informed of the commitment including a detailed description of the donor screening process and a stool donation protocol. The research staff will explain that a thorough clinical assessment and screening questionnaire will be completed. Volunteers will be informed that the questionnaire asks potentially sensitive questions

. They will be informed of the requirements to have laboratory blood work, including HIV testing, and stool studies and to submit stool specimens. The research assistant will orally describe the material written in the informed consent document and answer any questions the potential donor may have. Potential donors will be reminded that they are not required to participate in the study. Participants who give their consent will sign a copy of the document and will be given a signed copy of the informed consent document.

Protection against risk

Data and safety monitoring will take place to assure the safety of subjects. All participants will be reminded that their participation is voluntary and that they can withdraw at any time without penalty.

Additionally, the risks described above will be minimized by the following procedures:

1. We will minimize the risk of potential coercion by following standard procedures for obtaining informed consent from both subjects and stool donors. We will begin this process during the intake, where we will clarify the nature of the study and possible alternatives upfront. Prior to enrolling subjects in the research, we will fully explain the study procedures, risks, benefits, and alternatives, emphasizing that the subject's participation has no impact on the other services they receive. Also, subjects who do not consent or who withdraw during the study period will continue to receive appropriate treatment if needed. All subjects and donors will be reminded that there is no penalty for those who choose to not participate or to withdraw from the study and that their decision to participate does not impact the standard services they receive through the hospital. Subjects will not receive financial compensation for their participation. Volunteer donors will be paid a small stipend of \$40 per stool donation (to cover their time & burden of screening/stool collection).

2. We will minimize potential risks due to loss of confidentiality by having all information collected and handled by research staff trained to deal appropriately with sensitive clinical issues. Potential donors will also be informed about the risk of being ineligible to donate stool due to positive results on screening questionnaires or laboratory testing. Results of donor medical interview, screening and laboratory testing will be kept separate from subject data and only deidentified data will be available to the subject or his/her most responsible physician. All study information will be treated as confidential and will be available only to research staff. Hardcopies will be kept in locked file cabinets, and computer data files will be encrypted and available only to authorized personnel – with no storage of names or obvious identifying information. No participant will be identified in any report of the project. Further, when contacting participants for follow-up, no identifying information other than the first name of the research assistant will be used when leaving messages or speaking to anyone other than the participant him/herself. Written consent will be obtained to contact other persons for the purpose of locating the participant for follow-up and participants can refuse or revoke such consents. No information about participants will be released without their permission or where required by law.

3. We will minimize the theoretical risks of infectious disease or other conditions possibly transmitted through FMT by using donor screening protocols modeled after blood banks and organ transplant programs. Potential volunteer donors will undergo thorough screening to determine eligibility for donation. The primary purpose of the donor examination and interview is to ensure that the donor is in good health, and to identify risk factors for diseases transmissible by stool. The donor interview will be used to identify risks for diseases and conditions for which there are no laboratory tests, for which tests are not sensitive enough to detect infectious disease agents, and for tests unable to identify early stage or window period infections. Potential donors will be interviewed using a Donor Risk Factor Questionnaire (Appendix 2). Health status of donors will be monitored prospectively, and donors will be rescreened every 60 days.

4. We will minimize the risk of severe CDI recurrence by maintaining close clinical contact with all subjects. Subjects will be encouraged to contact the clinical team if they experience recurrence of diarrhea, fever, or abdominal pain – so that stool can be tested for *C. difficile* toxin if indicated, and antibiotics can be resumed if necessary. Subjects will be contacted via telephone by a Clinical Research Coordinator on Day 3, Week 6, Month 6 and Month 12. A clinical assessment will take place between Week 6 +/- 2 weeks. If any patient experiences recurrent CDI via FMP250 or FMP250E they would be eligible for a second FMT by colonoscopy using a different donor.

VII-E. Safety Monitoring Protocol

Safety monitoring plan

An external Data and Safety Monitoring Board (DSMB) will be assembled to evaluate the data and the safety of subjects enrolled in the study. The DSMB will consist of 3 physicians with specialization in gastroenterology and/or infectious disease. Initially, the Board will convene with the Principal Investigator to review the study protocol and guidelines for data and safety monitoring. This initial review will include establishing standard procedures for monitoring. At each quarterly meeting the DSMB will evaluate recruitment, the progress of the study, subject retention, data quality and confidentiality. The DSMB will review subjects' clinical status, adverse events and whether or not there have been any changes in risk to participating subjects. This quarterly review will ensure that subject risk does not outweigh study benefits. A report generated from each of these meetings will be retained at the study sites and will be forwarded to the IRBs and to the FDA (in accordance with Investigational New Drug (IND) regulations). The DSMB will be available to convene outside of the appointed meeting schedule if necessary, due to concerns regarding a particular subject, or due to any adverse events during the study. The DSMB will make appropriate recommendations for changes in the study protocol, if needed.

The safety of participants will be monitored for the duration of the study at each contact. Both anticipated and unanticipated adverse events and problems will be formally monitored and recorded. Unanticipated serious adverse events *related* to FMT material will be reported to the hospital and IRBs (as per local reporting requirements) and the FDA (within 15 days; or 7 days for unexpected fatal or life threatening events *related* to FMT material). Anticipated and less serious adverse events, as previously outlined, will be submitted annually in reports to the IRBs and FDA. The Principal Investigators will be responsible for monitoring the safety and efficacy of this study, executing the DSMB plan, and complying with the reporting requirements. The DSMB report will include the participants' sociodemographic characteristics, any quality assurance or regulatory issues that occurred during the past year, a summary of adverse events and serious adverse events, and any actions or changes with respect to the protocol.

VIII. Data Monitoring Plan

Data will be collected using standardized paper forms and will only be identified with the study's ID of the subject. The codes that link the name of the subject and the study ID will be kept confidential by the Site Investigator in a secured cabinet. Collected forms will be transported to the Site Investigator data entry center. Data will be entered in the REDCap computer database independently by trained data entry staff, and discrepancies will be corrected by the Site Investigator, based on source documents. Data quality will be monitored once per month by random inspection of the completed forms by a Clinical Research Coordinator; any problems detected will be discussed with the Principle Investigator. Telephone follow-up will be conducted by a Clinical Research Coordinator with data directly entered immediately into the REDCap computer database. Descriptive statistics will be computed periodically and reported in aggregate as part of the study monitoring process.

IX. Educational Training

Researchers and clinician Investigators involved in the study will need to have successfully completed an institutional human subjects research program/module. The principle Investigator will maintain documentation for all study personnel. For sites utilizing enema delivery, a Clinical Research Coordinator will be responsible for overseeing a brief enema session with site study personnel.

X. Potential Limitations

1. Correlational Safety Data

• This open-label, longitudinal cohort will not have an untreated arm. Thus, it will be difficult to compare the probability of a newly acquired adverse event compared to a control. Given that the patient population with recurrent CDI tends to be older with core comorbidities, they are at high risk for new medical conditions, new medications, and poor outcomes, which may or may not be related to FMT. Thus, it is difficult to discern if there is an increased probability over baseline risk. This study has purposefully limited the age to 50 and designed exclusionary criteria (e.g. severe underlying disease that the patient is not expected to survive for the next 1 year) to reduce noise and strengthen any signal. Where possible age matched, prognostic factor matched population data will be considered to determine if FMT material may present a statistically significant increase in risk of developing a serious adverse event. However, this will not be the primary aim, and the focus will be on capturing count data/rates for serious adverse events.

2. Stool Collection

• Patients will be collect his or her own stool samples and there may be potential error carrying out this procedure. Our study minimizes this risk with clear instructions, simplified process, clear labels, significant contact with study representatives, and reminder phone calls.

XI. Investigator Credentials and Associated Body Contact Information

Principal Investigator:	[name] [name]
Address:	[name]
Co-Investigator:	[name] PhD
Address:	[name]
Co-Investigator:	[name] PhD
Address:	[name]
Co-Investigator:	[name] MD
Address:	[name]

Co-Investigator:	[name] MD
Address:	[name]
Co-Investigator:	[name] MD
Address:	[name]
Co-Investigator:	[name] MD
Address:	[name]
IRB Name:	MIT IRB/COUHES
IRB Address:	[name]
Principal Investigator CV:	Appendix 7

XII. ClinicalTrials.gov Requirements

As required by law, this trial will be registered in ClinicalTrials.gov no later than 21 days after the first subject is enrolled. The reporting of summary results information (including adverse events) will be done no later than 1 year after the study completion date. The principle investigator will be responsible for registering the trial and results reporting.

